8.1.2.4 Depression Screening

Prevalence of Depression as per the Patient Health Questionnaire (PHQ-9) will be collected at 12 weeks. PHQ-9 Total Score Depression Severity Scoring is:

1-4	Minimal depression
5-9	Mild depression
10-14	Moderate depression
15-19	Moderate severe depression
20-27	Severe depression

8.2 Lumbar Puncture and CSF Analysis

8.2.1 Diagnostic Lumbar Puncture (LP) with Complete CSF Analysis

All patients with suspected meningitis will be screened for cryptococcosis by CrAg lateral flow assay (LFA). A CrAg LFA will initially be evaluated on whole blood obtained via fingerstick, with the results (return time = 10 minutes) directing subsequent work-up of CSF obtained by diagnostic LP. The screening informed consent process will be started after the fingerstick CrAg is collected. If the fingerstick CrAg is positive, a diagnosis of cryptococcal meningitis will be entertained and CSF studies will be directed to confirm/exclude this diagnosis. To evaluate for CM, a CrAg LFA will be performed on CSF obtained at the bedside during the LP procedure.

In cases of CM confirmed by bedside CrAg LFA, additional CSF studies will be obtained. Refer to the most current CSF Lab SOP on meningitis diagnostics. All LPs will be performed with manometers and have opening intracranial pressure (ICP) and closing pressure recorded. Quantitative fungal cultures will be performed. Remaining CSF samples will be stored at the site laboratory for future pharmacokinetic and pathophysiology studies.

If the screening fingerstick CrAg is negative, a diagnostic LP will be performed and non-specific CSF studies will be obtained to ascertain alternative diagnoses, refer to CSF Lab SOP for current details.

8.2.2 Therapeutic LPs with Quantitative Cultures

After cryptococcal diagnosis is known, follow up LPs will be performed to reduce ICP and document quantitative fungal culture to determine if the CSF is sterile. When an elevated opening CSF pressure is present (>20 cm H₂O), the therapeutic reduction of pressure is clinically indicated.^{62,63} We have previously demonstrated that a therapeutic LP conducted during the first week of therapy has a 70% relative reduction in mortality.⁴⁶

All follow up 'therapeutic LPs' will be analyzed for quantitative fungal culture. Should a persistent headache recur anytime during the study, a therapeutic LP must be recommended to decrease the intracranial pressure. These follow up therapeutic LPs require verbal consent of the participant per clinical practice.

8.2.3 Quantitative Fungal Cultures

Fungal cultures will be performed per the SOP: "Protocol for quantitative CSF microbiology cultures for *Cryptococcus neoformans*" as provided by Drs. [name] and [name].^{59,61} The quantitative culture SOP includes an undiluted, standard CSF fungal culture, the result of which will be used for CM management. Cryptococcal isolates will be frozen at $\leq -20^{\circ}\text{C}$ in cryovials with 1mL of 25% glycerol. The purpose of storing isolates is to enable external quality assurance and enable future susceptibility testing as needed. Cryptococcus isolates will be stored indefinitely.

8.2.4 Frequency of LPs

An initial LP is required for CM diagnosis at the time of enrollment with written informed consent. Therapeutic LPs will be performed at Day 3 ± 1 and Day 7 ± 2 , and whenever clinically indicated for the reduction of elevated ICP as recommended by IDSA and DHHS guidelines.^{62,63} Subjects with a positive CSF culture at Day 14 (estimated ~30%) will be recommended to have a follow up LP by the Week 4 outpatient visit to document whether ongoing culture positive cryptococcosis is continuing. Additionally, subjects with a positive CSF culture at Week 4 (estimated ~10%) will be recommended to have a follow up LP by the week 6 outpatient visit to document whether ongoing culture positive cryptococcosis is continuing.

The majority of individuals being treated for CM are expected to have sterile CSF cultures by Week 4. Those with ongoing CSF culture positivity should have follow up LPs to document clearance of the cryptococcal infection, prior to decreasing the fluconazole maintenance dosing. Until CSF is known to be culture negative, fluconazole should remain dosed at 800 mg/day.

Serial LPs are recommended as the standard of care for controlling elevated ICP in CM. According to the current standard of care, if a subject has elevated intracranial pressure

(>20 cm H₂O), an LP should be performed therapeutically to reduce elevated intracranial pressure.^{18,64} Therapeutic LPs conducted within the first one week of therapy have a ~70% relative reduction in mortality.⁵²

All follow-up LPs must have verbal consent from the subject prior to performing the LP per clinical practice. As LPs are invasive procedures, subjects will need to give consent prior to performing follow up LPs. The initial diagnostic LP at screening visit requires written informed consent. Follow up LPs require verbal consent. Subjects may decline follow-up LPs at their own risk, but at minimum will be offered therapeutic LPs at Day 3 ±1 and Day 7 ±2.

Once subjects are CSF culture negative (given at least 7 days of culture growth) and have a normal CSF opening pressure (< 20 cm H₂O), they should not have a routine follow up LP, unless new symptoms develop. If new symptoms develop concerning for CM-IRIS or CM relapse, an LP will be recommended for the subject for diagnosis to guide clinical management.

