4. STUDY DESIGN

4.1 Phase II Study Design

Figure 4.1

This is a single-arm trial with historical controls to compare the efficacy and safety of reduced dosing of 5-FC induction therapy for the treatment of cryptococcal meningitis in combination with IV AMB to standard of care, with EFA as the primary endpoint.

Participants will be enrolled into an investigational cohort at study entry.

1. The investigational cohort will receive 60mg/kg/day of 5-FC divided into 3 doses per day for 10 days, n~50 total enrolled to achieve n=36 CSF culture positive.
2. The control group will consist of historical participants in the AMBITION trial
3. All participants will receive liposomal Amphotericin B 10 mg/kg, single-dose infusion, if available.
4. If liposomal Amphotericin is unavailable, participants will receive IV amphotericin deoxycholate 0.7-1.0 mg/kg/day for 7 days.
5. All participants will receive fluconazole 1200 mg/day during induction therapy from day 1 to 14 then consolidation therapy 800 mg/day from day 15 to 10 weeks, and maintenance therapy of 200 mg/day after 10 weeks.
6. All participants will receive lumbar punctures at diagnosis, day 3, day 5-7, day 10-14, and additionally as required for control of intracranial pressure and documentation of CSF sterilization. Therapeutic LPs conducted during the first week have a ~70% relative survival benefit.

Investigational cohort will receive:

- IV Amphotericin B deoxycholate 1 mg/kg/day for 7 days or IV Liposomal Amphotericin B 10mg/kg single dose.
- Oral flucytosine (5FC) 60mg/kg/day for 10 days in 3 divided doses
- Oral fluconazole 1200mg/day from Day 1 to 14
- Oral fluconazole 800mg/day from Day 15 to Week 10
- Oral fluconazole 200mg/day thereafter

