6.1 Cryptococcal Meningitis Management

Medication management is summarized in Table 6.2, as per 2018 and 2022 cryptococcal WHO guidelines,^{4,58} which exceed the local standard of care.

Table 6.2: 2018 and 2022 WHO Treatment Regimen for Cryptococcal Meningitis

Medication and Dose	Week 1	Week 2	Week 3-10	Week >10
Amphotericin B (1.0 mg/kg/day) + flucytosine 100mg/kg/day ^a				
Fluconazole 1200mg daily				
Fluconazole 800mg daily				
Fluconazole 200mg daily				Through 12 months
Treatment Phase	Induction	Induction	Consolidation	Secondary Prophylaxis

Notes: ^a Flucytosine (5FC) 100 mg/kg/day preferred where available, otherwise fluconazole at 800–1200mg/day in divided doses with two weeks of amphotericin B. KCl 40–60 mEq/day should be given with amphotericin.

Individual patient factors often alter patient care and fluconazole dosage on an individual basis at physician discretion, such as acute renal failure, duration of cryptococcal culture positivity, CM relapse, medication intolerance, and hepatic P450 drug-drug interactions (e.g. rifamycin).

As well, some individuals will remain CSF culture positive after 14 days of amphotericin, thus higher dose fluconazole with fungicidal activity (1200 mg/day) may be used until outpatient clinic enrollment at Study Week 4. For persons with persistently positive cultures, refer to Section 7.4 on outpatient clinical management of CM. Induction therapy using a combination of amphotericin and either high-dose fluconazole or flucytosine is recommended as the microbiologic activity is greater than that of amphotericin alone. Subjects who remain CSF culture positive should continue on at least induction-dose fluconazole until culture negative.

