6.2.3 Fluconazole

Fluconazole is a synthetic triazole antifungal agent that is available in 200 mg oral tablets. Fluconazole is a white crystalline solid which is slightly soluble in water and saline. Diflucan tablets contain 200mg of fluconazole and the following inactive ingredients: microcrystalline cellulose, dibasic calcium phosphate anhydrous, povidone, croscarmellose sodium, FD&C Red No. 40 aluminum lake dye, and magnesium stearate.

Typical dosing is 200-1200 mg daily. Duration of dosage depends on severity of infection. The oral bioavailability of fluconazole is >90%.

Fluconazole is a highly selective inhibitor of fungal cytochrome P450 dependent enzymes. It is a potent CYP2C9 inhibitor and moderate CYP3A4 inhibitor. Thus, patients who are on fluconazole and other drugs metabolized through CYP2C9 and CYP3A4 should be monitored.

Acquisition: When available, fluconazole will be obtained from the Ministry of Health via the Pfizer Diflucan Donation Programme (as per standard clinical practice). Any GMP-manufactured fluconazole is acceptable.

Product Storage and Stability: Fluconazole needs to be stored below 86°F (30°C).

Study administration: Fluconazole is an oral medication, used for the treatment of many fungal infections including CM. After induction therapy, 800mg/day will be given until sterilization of CSF can be documented and effective ART is initiated, as outlined in Table 6.2. If there is fluconazole toxicity, the dose can be reduced to 400 mg/day for consolidation therapy after negative cultures for Cryptococcus have been documented. It can be further reduced to 200 mg/day after 10 weeks for secondary prophylaxis, assuming there is no reason to continue high dose fluconazole (history of CM relapse, CM-IRIS, concurrent fungal infection, or other reasons per medical officer clinical judgment).

The justification for the increased dose is based on recent studies that have shown that fluconazole is more potent and safely tolerated at higher doses.^{19,42,44,46} In a study from Mbarara, for example, Longley et al showed that fluconazole was more rapidly fungicidal when administered at a dosage of 1200 mg per day versus 800 mg per day.¹⁹ The current 2018 and 2022 WHO cryptococcal guidelines recommend 800 mg/day for 8 weeks during consolidation therapy (Week 3 to Week 10).^{4,58}

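### Sections 6.1 and 8.2.4 state different default fluconazole doses for participants still CSF culture positive after Day 14, and Section 7.4 does not settle which applies

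*Combined protocol and SAP*

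**What the plan says.** Four sections of the combined protocol and SAP bear on the fluconazole dose after induction.

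- Section 4.1 gives the schedule (the last figure quoted is in weeks): "All participants will receive fluconazole 1200 mg/day during induction therapy from day 1 to 14 then consolidation therapy 800 mg/day from day 15 to 10". It makes no exception for participants whose cultures are still positive.
- Section 6.1 is about those participants. It first permits a higher dose for a limited time: "higher dose fluconazole with fungicidal activity (1200 mg/day) may be used until outpatient clinic enrollment at Study Week 4". It then closes with a directive: "Subjects who remain CSF culture positive should continue on at least induction-dose fluconazole until culture negative".
- Section 6.2.3 says: "After induction therapy, 800mg/day will be given until sterilization of CSF can be documented and effective ART is initiated".
- Section 8.2.4, after discussing repeat lumbar punctures for people with persistent growth, says: "Until CSF is known to be culture negative, fluconazole should remain dosed at 800 mg/day".

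Section 6.1 sends the reader to Section 7.4 for persistently positive cultures. Section 8.2.4 estimates that about 30% will be culture positive at Day 14 and about 10% at Week 4.

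**The concern.** For a participant whose CSF still grows *Cryptococcus* after Day 14, Section 6.1 read with Section 4.1 sets a default of at least 1200 mg/day. Sections 8.2.4 and 6.2.3, and the schedule in Section 4.1, set 800 mg/day. Section 6.1 also differs within itself: 1200 mg/day is optional up to Week 4 in one sentence, while the induction dose is the expected minimum until clearance in another.

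Two things are at stake. The first is a dosing instruction that staff at three hospitals could read in different ways. The second is interpretation. This is a single-arm trial compared with historical controls, so post-induction fluconazole that varies by site or clinician would be a second source of variation in the later outcomes, alongside the 5-FC dose.

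**Working it through.** **1. Same people, same period.** The closing sentence of Section 6.1 covers participants who remain culture positive, until they are negative. The sentence in Section 8.2.4 covers participants until they are known to be negative. Everyone with a positive culture after Day 14 falls under both.

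**2. What the induction dose is in this trial.** Section 4.1 states "fluconazole 1200 mg/day during induction therapy from day 1 to 14". The synopsis gives the same 1200 mg/day for days 1 to 14, although it labels that period consolidation. The label is unstable, but the dose for those days is not.

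**3. The doses side by side, for a participant culture positive after Day 14.**

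- Section 6.1, directive sentence: at least the induction dose, so at least 1200 mg/day by Section 4.1.
- Section 6.1, permissive sentence: 1200 mg/day optional until Week 4.
- Section 4.1 schedule: 800 mg/day from Day 15 to Week 10.
- Section 6.2.3: 800 mg/day until sterility is documented and effective ART is started.
- Section 8.2.4: 800 mg/day until known negative.

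Difference between the two defaults: 1200 − 800 = 400 mg/day.

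**4. Does Section 7.4 settle it?** It sets repeat lumbar punctures at Weeks 4, 6, 8 and 10 for those not yet sterile. It gives no fluconazole dose for them at Weeks 4, 6 or 8. At Week 10 it steps down to 200 mg/day with a list of exceptions. Persistent culture positivity is not named, though the list ends with clinical judgment.

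**5. How many participants.** The 30% and 10% are planning estimates with no inputs shown, so they cannot be rebuilt and are taken as given. Section 8.2.4 does not state their denominator. Section 5.1 requires 36 culture-positive participants and allows up to 50 enrolled.

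- Applied to 36: 0.30 × 36 = 10.8, about 11, at Day 14; 0.10 × 36 = 3.6, about 4, at Week 4.
- Applied to 50: 0.30 × 50 = 15 and 0.10 × 50 = 5.
- If the 30% refers only to those culture positive at baseline, and 10–15% are culture negative at baseline (Section 5.1), the share of all enrolled is 0.30 × 0.90 = 27% to 0.30 × 0.85 = 25.5%. If all 50 are enrolled to obtain 36, it is 10.8/50 = 21.6%.

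**6. Which endpoints fall in the disputed period.**

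- Primary EFA is measured over about two weeks, essentially before the conflict begins.
- In the DOOR ranking, the split between the two survival tiers depends on sterility by two weeks, so it too is fixed beforehand. The survival component runs to 18 weeks.
- Sterility at 6, 10 and 18 weeks, 18-week survival (Section 11.5) and the 10-week survival comparison with controls (Section 4.1) all fall after Day 14.

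**The case against.** The best defence is that the sections share a purpose. The sentence before the one quoted from Section 8.2.4 speaks of documenting clearance before the maintenance dose is lowered, so the 800 mg/day may be a guard against stepping down too soon. Section 6.2.3 likewise ties a toxicity-driven reduction to documented negative cultures. On this view every section forbids a step-down while cultures are positive. That reading is fair as to intent. But Section 8.2.4 names a dose to remain on, not a minimum, and Section 6.1 sets a different minimum.

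A second defence is that the induction dose need not mean 1200 mg/day, because the note to Table 6.2 reads "otherwise fluconazole at 800–1200mg/day in divided doses with two weeks of amphotericin B" and 800 mg/day would then satisfy Section 6.1. That note describes regimens without flucytosine. This trial gives flucytosine and sets its own figure in Section 4.1, so the reading is arguable but not the natural one.

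A third is discretion. Section 6.1 lets physicians alter the fluconazole dose for individual reasons and lists duration of culture positivity among them. This stands against a stronger reading that someone might infer, that staff cannot comply with the protocol at all. The latitude is written in, and the text does not support that reading. Discretion still needs one default to depart from, and here there are two.

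Finally, Section 5.1 says cultures take 7 to 14 days to report, so a Day 14 result may not be known when the dose changes on Day 15. That shortens the time over which the conflict applies but does not remove it once the result arrives.

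**Conclusion.** The inconsistency is real and sits in the current text: two defaults, 400 mg/day apart, for one group of participants. The conclusion assumes that the dose in Section 4.1 defines the induction dose. On the protocol's own estimates it concerns about 11 to 15 participants at Day 14 and about 4 to 5 at Week 4, depending on which of the two denominators is used.

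Its reach is limited. The primary EFA result is essentially unaffected. The later sterility and survival endpoints could be affected if sites apply different sections, but Section 11.7 describes the secondary endpoints as mainly descriptive.

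Three larger claims that a reader might infer are not supported:

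- That 30% of the cohort is affected throughout. The figure is for Day 14, has no stated denominator, and falls to about 10% by Week 4.
- That these are the sickest participants. The documents show only that they are slowest to clear, and Section 2.5 reports relatively higher mortality among people with sterile cultures as well.
- That the comparison with AMBITION controls is biased. The documents do not say what controls received if still culture positive after Day 14, so neither the presence nor the direction of a difference can be established.

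**What to change.** Reconcile Sections 4.1, 6.1 (both sentences), 6.2.3 and 8.2.4 so that one default instruction applies to participants culture positive after Day 14, and repeat it in Section 7.4, where staff are sent for guidance. Use one label for the Day 1 to 14 period in the synopsis and Section 4.1, so that a reference to the induction dose has a single meaning. Which dose is right is for the clinical team.

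On the analysis side, add a descriptive summary of the fluconazole dose given after Day 14 to participants who were still culture positive. Section 13.1 already has medications recorded on the Med CRF, so no new data collection is needed for the trial cohort. The cost is a protocol clarification and one additional table.

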8.3 Laboratory Evaluations

All routine clinical tests as specified on the schedule of events will be performed at the local site lab. Print out of lab results will be placed into research charts.

8.3.1 Hematology

CBC monitoring will be encouraged as part of routine care at the start of induction antifungal therapy, initial evaluation for ART, and whenever clinically indicated. Scheduled draws will occur at enrollment, Day 5-7, Day 14, and Week 6.

8.3.2 Chemistry

Serum creatinine, sodium, potassium, and ALT, total-bilirubin will be monitored at the local approved site laboratory as part of routine care at the start of CM therapy, initial evaluation for ART, and whenever clinically indicated. Serum aliquots of 0.5-1mL will be frozen at -80°C. An estimated creatinine clearance can be obtained using the Modification of Diet in Renal Disease (MDRD) Study equation:⁶⁵

$$\text{GFR (mL/min/1.73 m}^2\text{)} = 175 \times (\text{Scr}) - 1.154 \times (\text{Age}) - 0.203 \times (0.742 \text{ if female}) \times (1.212 \text{ for African})$$

8.3.3 CD4 Profile

CD4 profiles will be encouraged on initial HIV diagnosis as part of routine care and at 10 weeks.

8.3.4 Stored Specimens

Any extra serum and plasma collected for clinical testing (e.g., creatinine and potassium) will be stored for later potential cytokine analysis (Bio-Rad, Hercules, CA) via a Luminex Magpix instrument to investigate biomarkers which predict risk of mortality and/or IRIS pathogenesis. The volume of stored blood should always be < 30mL for all pathogenesis studies.

The CSF supernatant will be frozen for pharmacokinetic and pathogenesis studies.

If a subject later withdraws storage consent (after initial consent), their study chart should be marked for 'No Storage,' and the PIs notified in order to destroy any stored specimens.

8.4 Specimen Storage

Specimens processed at the study site will be per the laboratory protocols for the site lab for clinical tests. Extra serum, plasma, and CSF must be stored at -80°C.

8.5 Biohazard Containment

Appropriate blood and secretion precautions will be employed by all personnel during blood draws, lumbar punctures, and shipping and handling of all specimens for this study, as currently recommended by the CDC, the NIH, and national guidelines.

9. ASSESSMENT OF SAFETY

This is a clinical trial investigating whether a lower dose of flucytosine is safe and effective compared to standard dosing. There is evidence that lower doses reach adequate levels above MIC for *Cryptococcus*.

Participants will also receive fluconazole and/or Amphotericin B as well as HIV therapy and cotrimoxazole. HIV therapy will be provided via the public health system. This study will provide antifungal therapy while hospitalized, if otherwise unavailable. Outpatient standard of care fluconazole will be provided by this research study.

9.1 Adverse Event (AE) Definitions

The intervention during this trial is the reduced dose of flucytosine for induction therapy.

Adverse Event (AE)

An AE is any untoward medical occurrence in a clinical investigation subject administered a pharmaceutical product and which does not necessarily have to have a causal relationship with this treatment. An AE can therefore be any unfavorable or unintended sign (including abnormal laboratory findings), symptom, or disease temporally associated with the use of a medicinal product. Any symptom, sign, illness or experience that develops or worsens in severity during the course of the study are considered AEs.

Any medical condition already present at the time of screening should not be reported as an adverse event unless the medical condition or signs or symptoms present at baseline changes in severity or seriousness at any time during the study. In this case, it should be reported as an adverse event.

As a diagnosis may have multiple signs or symptoms associated with the AE (e.g., sepsis presenting with fever, hypotension, confusion), a single diagnosis for the AE is preferred over reporting each individual symptom.

Clinically significant abnormal laboratory or other examination (e.g., ECG) findings that are detected during the study or are present at the time of screening and significantly worsen during the study are defined and should be reported as adverse events. The Investigator will exercise his or her medical and scientific judgment in deciding whether an abnormal laboratory finding, or other abnormal assessment is clinically significant. Clinically significant abnormal laboratory values occurring during the clinical study will be followed until repeat tests return to normal, stabilize, or are no longer clinically significant. Any abnormal test that is determined to be an error does not require reporting as an adverse event. Laboratory abnormalities will be separately categorized from clinical AEs.

Worsening of the index indication (cryptococcal meningitis) due to insufficient therapeutic effect of study drug is captured as an efficacy measure (i.e., death, poor early fungicidal activity) and in general will not be considered an adverse event but are captured in other individual trial endpoints. As participants enter the trial with Grade 4 cryptococcal meningitis, worsening is not possible, unless death occurs.

